In this double-blind, placebo controlled, randomized trial, individuals with OUD (*N*=50) who are currently receiving treatment with buprenorphine/naloxone or methadone will be randomized to intranasal oxytocin (40 international units, IU) and oxytocin-matched placebo, administered twice/day for 7 days with a minimum of two days between the opposite condition (oxytocin or placebo). On days 5 and 7, and on days 14 and 16, participants will complete two counter-balanced sessions in which they receive yohimbine (32.4 mg) or yohimbine-matched placebo, and responses to opioid cues are assessed.

Aim 1: assess the effects of oxytocin on cue-induced opioid craving after yohimbine stress-induced. We hypothesize that opioid craving will be reduced in the oxytocin condition, compared to the oxytocin-matched placebo, after yohimbine stress induction.

Aim 2: assess whether baseline levels of stress affect the effects of oxytocin on cue-induced opioid craving after yohimbine-matched placebo. We hypothesize that after yohimbine-matched placebo administration, opioid craving will be reduced in the oxytocin condition only among individuals with higher levels of stress at baseline.

Aim 3: to assess the safety and tolerability of oxytocin and yohimbine in OUD individuals receiving buprenorphine/naloxone or methadone. Participants will complete a laboratory session that includes a battery of medical/physiological/psychological assessments to monitor adverse events.

Aim 4:

Exploratory Aims: we will examine the effect of oxytocin, as compared to placebo, on neuroendocrine fluctuations of salivary cortisol (three points area under the curve) and blood neurotensin, orexin and substance P by comparing hormones concentrations at baseline and after study medication and placebo administration (visit 3, 4, 5 and 6).

This research will be the first to assess the clinical efficacy of repeated oxytocin administration to prevent opioid stress-induced relapse. Considering the high comorbidity between OUD, anxiety disorder and PTSD, this proposal will pave the avenue for testing oxytocin as an adjunct opioid replacement therapy (ORT) for an as needed personalized pharmacotherapy for this population.

[figure not shown]

If your study ONLY involves the use of identifiable secondary data / biospecimens, including coded data from which you may be able to ascertain identity, skip to PART VI. Otherwise, please continue.

3. Materials, Methods and Analysis.

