- Current substance disorder other than marijuana, nicotine and caffeine as assessed by self-report and urine toxicology screen at baseline;
- Current use of medications that may interact with study medications;
- History of hypersensitivity to study medications;
- Clinically significant electrolyte abnormalities, current rhinitis or use of vasoconstricting medications or prostaglandins.

NOTE: the exclusion criteria are based in reducing participants' safety.

Participants need to speak English and be able to understand informed consent and questionnaires in English which will be written exclusively at an 8th grade level.

One hundred individuals receiving buprenorphine/naloxone or methadone as opioid replacement therapy (ORT) will be screened, 80 will be randomized, with 50 expected to complete the study. Potentially eligible participants will be invited for an in-person screening, where they will provide written informed consent and undergo a physical examination in the NEW Clinical Laboratory Core (CLC).

The **sample size estimate** is based on recent findings reporting that baseline levels of stress significantly predicted oxytocin effects on cue-induced craving (Mitchell et al., *J Addict Med*, 2016). Effect sizes were calculated based on a between-subjects in oxytocin study with alcohol related responses (Pedersn et al., *ACER*, 2013). The estimate of opioid craving (measured by the OCQ) were calculated from the *M* and the *SD* of alcohol-related outcomes: oxytocin was superior to placebo in reducing alcohol withdrawal (*i.e.* less lorazepam required to complete detoxification: 3.4 mg±4.7, vs. 16.5 mg±4.4, p<0.01), lower mean CIWA scores (4.3 mg±2.3 vs. 11.8 mg±0.4, p<0.01). We estimated that with a standard threshold, α = 0.05, for med-large effect (f = 0.35), two group independent variable and three covariates in ANCOVA, the *N* is 67 to detect 0.80 power. With an additional 0.20 to account for attrition [N = 50 (completers) + 13 = 80 (enrolled)]. The estimated power at N = 67, with the addition of an interaction term (for Aim 2) would be = 0.63. Therefore, the calculated sample size is well powered to address the hypothesis of the main medication effect (Aim 1) and of the interaction effect with stress and anxiety (Aim 2).

5. Recruitment Methods

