- Yohimbine: The oral dose of yohimbine for this study is based on prior studies, in particular from an ongoing study of [name] (PI and IND holder: NCT: 02243709; IND: 121984) in which yohimbine was administered to examine neuroendocrine probes in human studies. Ample data supports the safety of vohimbine to induce craving in alcohol-dependent individuals, and the safe induction of stress in PTSD veterans and gamblers. In this study, yohimbine (32.4mg), formulated by Bayview Pharmacy is administered below the therapeutic index to a dose considered unsafe (>100mg). Furthermore, yohimbine will be administered only once, during the laboratory session and under direct supervision of the study personnel. It will be given at a safety-tested dose to increase noradrenergic activity already being evaluated in psychiatric patients with clinically relevant stress conditions such as PTSD, anxiety, and depression. Finally, yohimbine's short half-life ($t_{1/2}$ = 1-2 hour) provides a transient effect. The protocol includes close monitoring of vital signs (BP, HR and MAP) and cortisol levels. [name] and/or the CADRE NP will evaluate any possible adverse effect due to yohimbine administration. In addition, we will administer the standardized CADRE assessment to determine stress and anxiety at baseline. If anxiety is higher at the end of the study we will call [name] and/or the CADRE NP to have him meet with the patient before being released. The most common side effects reported by the use of yohimbine are: an allergic reaction, irregular or fast heartbeat, confusion, dizziness, anxiety, irritability, or nervousness, tremor, headache, skin flushing and we have not encounter these effect in our ongoing trial (PI and IND holder: NCT: 02243709; IND: 121984).

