The ITT analysis was suitable for this crossover design ³ as the placebo condition was treated identically to the active drug condition (route, administration and laboratory procedures). Distributional characteristics of outcome measures were examined to evaluate similarity to the normal distribution. detailed descriptive analysis of demographics, substance use, and clinical characteristics. The cortisol had a kurtosis in excess of four; consequently, an outlier analysis was performed and a total of 5 outliers falling outside of ±3 interguartile range were Winsorized as recommended ⁴. Comparisons with these characteristics, in relation to enrolled versus completer status, were performed using *t*-tests to analyze continuous variables (age) and χ^2 for categorical variables (sex, race, medication status). Attrition rates between the screening visit and follow-up visit were examined descriptively to assess for potential bias. In addition, a logistic regression was performed to test for possible bias due to period (placebo first, then oxytocin and oxytocin first, then placebo) or medication carryover (placebo and oxytocin), as done in our prior cross-over trial ⁵. This study tested the feasibility of the combined study design, the safety and tolerability of IN oxytocin and yohimbine, and the potential value of testing IN oxytocin as adjunct therapy in an appropriately-powered larger RCT. In selecting a target sample size, we balanced power considerations and feasibility given the preliminary nature of this trial. Because of the within-subjects design, power to test the effects of the study drug was optimized for this modest sample size. For the safety and tolerability outcomes (primary) adverse events, difference was detected based on a

judgement concerning the minimal effect, which has clinical relevance in the management of patients. In a noninferiority trial, the exact sample size could not be fixed in advance because it depends upon the chosen stopping guidelines ⁶.

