Outcomes: Primary (craving) and secondary (safety and tolerability) outcomes were assessed in realtime in the laboratory. Seven-day oxytocin administration was compared to the oxytocin-matched placebo condition during the CR procedure, in which noradrenergic activation produced by yohimbine or yohimbinematched placebo condition (2X2 design) was measured. We used Generalized Linear Model (GLM) with modelbased estimator in the covariance matrix, with medication (oxytocin/placebo) and noradrenergic activation (yohimbine/placebo) as within-subject factors. The model was specified to evaluate the effect of drug (oxytocin/placebo) by noradrenergic (vohimbine/placebo) interaction, main effect of the drug, and main effect of noradrenergic activation. Craving was assessed using the DDQ with time coded as: t_0 =relaxation, t_1 =interaction with drug paraphernalia/opioid auditory cues and t_2 =opioid use video. Safety and tolerability were assessed using: SBP, DBP, HR (vital signs), HAM-A and STAI (anxiety). The STAI y1 (state) was included as an additional safety measure for anxiety to ensure participants were not experiencing acute symptoms of anxiety within the laboratory. The STAI y2 (trait) was inserted as a covariate in the model to control for baseline anxiety level, along with stress (PSS), HPA (cortisol), and noradrenergic response (α -amylase). Time at laboratory sessions was coded as: t_0 =baseline, t_{45min} =45-min after yohimbine administration, and t_{90min} =post cue-exposure to specifically evaluate the contribution of each laboratory procedure (vohimbine and CR). Withdrawal symptoms (COWS) and AEs were assessed at specific timepoints: t_0 =pre-laboratory and t_1 =post-laboratory procedures.

Other outcomes (safety and tolerability) were measured retrospectively during the one-week outpatient setting and included the: COWS (withdrawal), anxiety (HAM-A and STAI), stress (PSS), depression (HAM-D) and AEs. The other outcomes were analyzed using ANOVA test and the number of AEs via a χ^2 test. For missing data approach, we first categorized missing data as missing completely at random (MCAR), missing at random (MAR) or missing not at random (MNAR)⁷. Analysis with GLM (using all available pairs of data to model missing values with maximum likelihood estimation) was deemed suitable for our analyses because no systematic differences existed between participants with missing data and those with complete data (MCAR)⁸.

Missing data reporting ⁹

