- 1. Amount of missing data in the dataset:
 - a. Oxytocin condition: 10% did not receive either oxytocin or placebo condition (within subject, *n*=16; between subject, *n*=4)
 - b. Yohimbine condition: 11.12% did not receive yohimbine condition (yohimbine, *n*=14; placebo, *n*=16; no yohimbine, *n*=4):

- 2. Reason for missing:
 - a. Oxytocin condition: change from between subject to within subject design
 - b. Yohimbine condition: safety concerns due to past history of cardiovascular disease and/or current hypertension (*n*=3), stroke (*n*=1)

3. Consequences:

- a. *Oxytocin condition*: no differences between participants with and without missing values except there were no subject taking methadone in the subjects with missing values.
- b. *Yohimbine condition*: no differences between participants with and without missing values except there were cardiovascular concerns in the subjects with missing values.
- 4. *Method*: GLM with MNAR using all available pairs of data to model missing values with maximum likelihood estimation
- 5. Software: IBM SPSS Statistics for Windows, version 29 (IBM Corp., Armonk, NY, USA)

All statistical analyses were performed after participants had completed their follow-up visits and the study database had been locked. The results were presented using summary statistics: number of subjects (n); mean (M); standard deviation (SD) or frequency distributions (%) and effect size was reported as Cohen's d.

All statistical procedures were performed by IBM SPSS Statistics for Windows, version 29 (IBM Corp., Armonk, NY, USA), and GraphPad Prism (v.10) was used to generate figures (La Jolla, CA, USA). All statistical tests were two-tailed, and statistical significance was accepted if an alpha value p<.05 was obtained.

References

1. FDA. Changes or modifications during the conduct of a clinical investigation; final guidance for industry and CDRH staff. 20012001.

Schulz K, Altman D, Moher D. Consolidated Standards of Reporting Trials Group CONSORT
2010 Statement: Updated Guidelines for Reporting Parallel Group Randomised Trials. Bmj.
2010;340:c332.

4. Tukey JW. The future of data analysis. The annals of mathematical statistics. 1962;33(1):1-67.

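### Protocol Aim 2, whether baseline stress changes the oxytocin effect on craving, has no test in the SAP, and the SAP does not say that the aim was dropped

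*SAP*

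**What the plan says.** **Protocol, Part III, section 2 (Aim 2).** The hypothesis concerns yohimbine-placebo sessions and states that "opioid craving will be reduced in the oxytocin condition only among individuals with higher levels of stress at baseline".

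**Protocol, Part III, section 4 (sample size).** Power at N = 67 "with the addition of an interaction term (for Aim 2) would be = 0.63". The closing sentence of that paragraph names stress and anxiety as the variables in the Aim 2 interaction.

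**Protocol, Part III, section 7 (Yohimbine).** A baseline measure is planned through the "standardized CADRE assessment to determine stress and anxiety at baseline".

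**SAP, Statistical analysis, Outcomes.** Craving (DDQ) is recorded at t0 (relaxation), t1 (paraphernalia and auditory cues) and t2 (opioid use video). The GLM has oxytocin and yohimbine as within-subject factors and evaluates their "interaction, main effect of the drug, and main effect of noradrenergic activation". Trait anxiety enters as a covariate "along with stress (PSS), HPA (cortisol), and noradrenergic response" (alpha-amylase). The sentence refers to the model without naming its outcome.

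**SAP, Statistical analysis, purpose.** The study is to inform the "potential value of testing IN oxytocin as adjunct therapy in an appropriately-powered larger RCT".

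**The concern.** Aim 2 is a question of effect modification: does the oxytocin-minus-placebo difference in craving depend on a participant's stress before treatment? Answering it needs a term, or a subgroup comparison, that lets that difference vary with stress. The protocol foresaw such a term and the SAP has none.

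The stake is interpretation. A reader looking for the Aim 2 result could take the PSS coefficient, or a null overall oxytocin effect, as the answer, and it would be wrong to use either. The SAP presents the study as groundwork for a larger trial. Whether that trial should select or stratify on stress is a design decision that an interaction estimate, even an imprecise one, would inform.

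**Working it through.** **1. Search of the SAP for an Aim 2 test.** Each method, and what it addresses:

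| SAP method | Question addressed | Lets the oxytocin effect vary with stress? |
|---|---|---|
| GLM, oxytocin × yohimbine | Does the randomised challenge change the oxytocin effect? | No |
| GLM, two main effects | Average effects | No |
| PSS, STAI trait, cortisol, alpha-amylase as covariates | Level adjustment | No |
| t-tests, chi-square | Enrolled versus completers | No |
| Logistic regression | Period or carryover bias | No |
| ANOVA, chi-square | Outpatient safety outcomes, AE counts | No |

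There is no stress subgroup and no contrast limited to yohimbine-placebo sessions.

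**2. Why the model as written cannot answer Aim 2.** Let O = 1 for oxytocin, Y = 1 for yohimbine, S = baseline stress. If the covariates belong to the craving model:

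craving = b0 + b1·O + b2·Y + b3·O·Y + b4·S

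The oxytocin effect at Y = 0 is b1, the same for every S. The coefficient b4 says whether stressed people crave more. It does not say whether oxytocin helps them more. If S is not in the craving model, stress plays no part in it at all.

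**3. What would answer it.**

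craving = b0 + b1·O + b2·Y + b3·O·Y + b4·S + b5·O·S + b6·Y·S + b7·O·Y·S

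- Oxytocin effect at Y = 0: b1 + b5·S
- Oxytocin effect at Y = 1: (b1 + b3) + (b5 + b7)·S

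With yohimbine-placebo as the reference level, Aim 2 is b5. If only O·S is added to the pooled model, its coefficient averages the two slopes (b5 + b7/2 with equal numbers of sessions), and that is not Aim 2. Restricting the analysis to Y = 0 sessions targets b5 directly.

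**4. What the data could deliver.** The SAP's Missing data reporting section, in the item stating that "10% did not receive either oxytocin or placebo condition", gives 16 within-subject and 4 between-subject participants. Only the 16 can supply an oxytocin-minus-placebo pair. Regress that within-person difference on baseline stress, assuming bivariate normality, two-sided 0.05, and n − 2 degrees of freedom. The correlations r are assumptions, because the documents give none.

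| Usable pairs (n) | Power, r = 0.3 | Power, r = 0.5 | r needed for 0.80 |
|---|---|---|---|
| 16 | 0.21 | 0.53 | 0.64 |
| 14 | 0.18 | 0.47 | 0.67 |
| 12 | 0.16 | 0.40 | 0.71 |

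The rows for 14 and 12 are illustrations, not bounds.

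95% intervals at n = 16 by Fisher z, with half-width 1.96/√(16 − 3) = 0.544:

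- r = 0.3: z = 0.310, from −0.234 to 0.853, so r from −0.23 to 0.69
- r = 0.5: z = 0.549, from 0.006 to 1.093, so r from 0.01 to 0.80

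The protocol's 0.63 belongs to a between-subjects ANCOVA at N = 67. It is cited here only as evidence that an interaction test was intended.

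**The case against.** **The oxytocin-by-yohimbine interaction already covers stress.** It does not. Yohimbine is a randomised challenge, whereas Aim 2 concerns a participant's own stress before treatment, in the sessions without that challenge.

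**The sample is too small for the test to matter.** Much of this stands. With 16 pairs and r = 0.3 the interval covers zero and most plausible values, so the analysis can seldom settle Aim 2. The SAP's statement of purpose lists feasibility, safety and tolerability, and potential value for a larger trial, and does not list moderation. Low power is a reason to label the result exploratory or to say that the aim is not pursued. The SAP does neither.

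**Choosing a moderator now is post hoc.** This also stands. The protocol names no stress scale for Aim 2, PSS is not in its Table 1 of assessments, and the SAP already reports features of the data. Fixing one measure before the run limits selection but does not restore prespecification.

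**Stronger readings.** A reader might infer that the oxytocin estimate is biased by the stress covariates. The documents do not support that: the SAP does not name the outcome of the model that carries them, or say when PSS, cortisol and alpha-amylase were taken. A reader might also infer that Aim 2 was withdrawn on purpose. Nothing in the SAP says so, and it is simply silent.

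**Conclusion.** The point holds as an omission. A stated aim, with an interaction term planned in the protocol, has no corresponding SAP analysis and no statement that it was dropped. This rests on reading the two documents together. It does not depend on whether the covariates sit in the craving model, since an additive term cannot test moderation in either case.

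The omission does not invalidate the SAP's oxytocin, yohimbine or interaction tests. Nor does it follow that adding the term would have given a firm answer. Power is about 0.21 to 0.53 for assumed correlations of 0.3 to 0.5 if all 16 within-subject participants contribute a pair, and lower otherwise. The SAP does not report how many participants had a yohimbine-placebo session under both oxytocin conditions, so the number of usable pairs is unknown. The change is worth making because it costs little and prevents a wrong reading of Aim 2.

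**What to change.** Do one of the following.

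1. **Add an exploratory Aim 2 analysis.**
   - *Outcome:* cue-induced craving, DDQ at t1 and t2 relative to t0.
   - *Model:* oxytocin × baseline stress, either in yohimbine-placebo sessions only, or in the full model with the stress main effect, oxytocin × stress, yohimbine × stress and oxytocin × yohimbine × stress, reading the oxytocin × stress effect at yohimbine-placebo.
   - *Moderator:* one measure taken before first dosing and fixed before the run. Use PSS if a baseline value exists, otherwise the baseline CADRE stress measure.
   - *Reporting:* the number of usable pairs and the estimate with its 95% interval, labelled post hoc and exploratory, beside the original model.
2. **Or state plainly that Aim 2 is not tested**, and that no covariate coefficient or overall oxytocin effect should be read as its result.

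The first option costs one SAP paragraph and a rerun on data already held. Its price is an imprecise estimate with a post hoc label. The second costs a sentence.

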laboratory procedures (stress-induction). See below additional consideration to prevent the additional risks:

- JB Pharmacy will provide the oxytocin (40 IU intranasal) and yohimbine (32.4 mg, oral) that will be administered at CAAS under team supervision prior to the laboratory session. Risks of medications will be minimized through careful and detailed screening of participants by the PI, ([name]) who is a trained pharmacist and pharmacologist and the co-I, and study physician ([name]) who is a practicing physician and addiction psychiatrist, to minimize recruitment of those who might be at higher risk for adverse events, as well as careful and detailed monitoring of adverse events and participant well-being during the study.
- Oxytocin. There are usually no side effects in individuals that administer intranasal oxytocin spray at the dose provided in this proposed project. The half-life of intranasal oxytocin in serum is 3-17 minutes and therefore side effects should be minimal. Common side effects include: relaxation, irritability and stomach cramps. Less common side effects that are reported at higher doses include: mild dizziness, dry mouth, nausea, vomiting, nasal irritation, runny nose, or tearing of the eyes are common with medication given by nasal spray. Participants will be instructed on how to properly administer the nasal spray by the CADRE NP, with an empty sprayer bottle. The participant will administer the first dose while at the CADRE laboratory to ensure correct administration. Participants will be instructed to stop taking the medication and to call the PI if any side effects or adverse events as a result of the medication occur. The PI will then contact [name] and/or the CADRE NP who will recommend next steps. Participants may withdraw from the study at any time if they do not feel comfortable administering the medication and will be compensated for sessions that they have completed. To protect against or minimize any risk associated with opioid craving after the opioid cue-reactivity task, participants' vital signs and opioid craving with behavioral assessments will be monitored. If a clinically significant increase in craving were to occur, participants may require clinical management. [name] and/or the CADRE NP will be immediately called and will evaluate each participant on a case-by-case scenario.

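### Stopping or leaving because of side effects is not a tolerability outcome, and scheduled tolerability data after Visit 2 need attendance from Day 5 on, so the oxytocin-placebo comparison can miss the least tolerant participants

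*SAP*

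**What the plan says.** Aim 3 of the protocol is the safety and tolerability of oxytocin and yohimbine. The SAP (Statistical analysis) says the study also informs whether oxytocin merits a larger trial. It calls the safety outcomes primary in one paragraph and secondary in the Outcomes paragraph.

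**Measures.** For the laboratory sessions: "Safety and tolerability were assessed using: SBP, DBP, HR (vital signs), HAM-A and STAI (anxiety". Also: "Withdrawal symptoms (COWS) and AEs were assessed at specific timepoints", namely before and after the laboratory procedures. For the week at home: "Other outcomes (safety and tolerability) were measured retrospectively during the one-week outpatient setting", covering COWS, HAM-A, STAI, PSS, HAM-D and AEs. On analysis: "The other outcomes were analyzed using ANOVA test and the number of AEs" by a chi-square test.

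**Stopping.** The oxytocin paragraph of protocol Part III, section 7, says: "Participants will be instructed to stop taking the medication and to call the PI if any side effects or adverse events" result from it. The PI then contacts the clinician. The same paragraph allows withdrawal at any time.

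**Losses.** Protocol Part III, section 4, expects that "80 will be randomized, with 50 expected to complete the study". The SAP says: "Attrition rates between the screening visit and follow-up visit were examined descriptively to assess for potential bias". Under Missing data reporting, the only reason given for a missing oxytocin or placebo condition is "change from between subject to within subject design". The ITT set is everyone who took one dose or more.

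**The concern.** Giving up a spray because of its side effects is the most direct sign that it is not tolerated. In this plan that event is not an outcome, and it can also remove the participant from the scheduled outcomes that are analysed. The oxytocin-placebo comparison then rests largely on people who stayed on study.

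The Outcomes paragraph justifies using all available data by declaring the missing values MCAR. Loss caused by side effects would not be MCAR, and the Missing data reporting section itself names MNAR. What is at stake is a tolerability conclusion meant to inform the decision on a larger trial.

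**Working it through.** **1. When tolerability is scheduled.** The spray is dispensed on Day 1 (Visit 2), and the first dose is taken in the laboratory. The next visit is Day 5 (Visit 3). Protocol Table 1 places the Adverse Events Evaluation at Visits 2 to 7 and Visit B, and has no early-termination visit. AEs, COWS and HAM-A are scheduled at Visit 2, but whether before or after the first dose is not stated. Table 1 does not list PSS and shows HAM-D only at screening and Visit A. For those two, on-treatment collection is known only from the SAP, which describes no remote collection.

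**2. What each path off the spray leaves in the data.**
- Leaves between Day 1 and Day 5: in the ITT set, with no on-treatment laboratory value and no retrospective rating of the week at home. Any AE depends on a telephone call being recorded and counted.
- Leaves between the two courses: values for one spray only.
- Stops the spray but attends: scored while off the spray, which dilutes the contrast.

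**3. Whether another analysis catches this.** Attrition is counted from screening, so loss before dosing is mixed with loss on a spray, and it is not split by spray or reason. The enrolled-versus-completer comparison names age, sex, race and medication status. The logistic regression addresses period and carryover.

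**4. The plan's own figures.**
- Missing oxytocin condition: 16 participants had both conditions and 4 had one. That is 4 missing out of 20 × 2 = 40, or 10%, which reproduces the SAP's figure. All four are put down to the design change. The section does not say whether other dosed participants left.
- Planned loss: (80 − 50)/80 = 37.5%. This is non-completion for any reason up to Visit 7 on Day 20. The 80 is itself unclear: the protocol allows 20% attrition and writes 50 + 13 as 80, whereas 50/(1 − 0.20) = 62.5, rounded up to 63 = 50 + 13.

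**5. Possible size (assumed inputs only).** Let p be the true proportion intolerant on a spray, and k the share of them who leave unscored. The proportion seen among those scored is p(1 − k)/(1 − pk). Take p = 20% on oxytocin and 10% on placebo, with the same k on both:

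| k | oxytocin seen | placebo seen | difference seen (true: 10 points) |
|---|---|---|---|
| 25% | 15.8% | 7.7% | 8.1 |
| 50% | 11.1% | 5.3% | 5.8 |
| 75% | 5.9% | 2.7% | 3.2 |
| 100% | 0% | 0% | 0 |

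If p is 20% on both sprays and k is 50%, both show 11.1%. The difference is then unbiased at zero, but each spray looks better tolerated than it is.

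**The case against.** Several stronger readings are tempting, and the documents do not support them.

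- **That 30 of 80 participants have no tolerability score.** The 30 are planned non-completers for any reason. Anyone who leaves after Day 5 already has laboratory data. No document says how many leave between Day 1 and Day 5.
- **That tolerability rests only on physiological and anxiety readings.** AEs are counted too, including those from the week at home.
- **That everyone who stops goes unscored.** Stopping the spray is not leaving the study. The instruction to telephone is an unscheduled route for reporting AEs, and nothing excludes those reports from the count. AE handling may be set out in the Data and Safety Monitoring Plan or the medication management attachment, neither of which is available here.
- **That oxytocin was in fact made to look better.** The same blinded instruction applies to both sprays, so a biased difference needs intolerance to differ between them. No rate is given for either. In the dataset that the SAP describes, no missing oxytocin or placebo condition is left to attribute to intolerance.

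These objections limit the size of the point but do not remove it. Identical rules still shrink a real difference, as the table shows. The SAP does not say that telephoned AEs count. Even if they do, someone who left before Day 5 has no on-treatment vital signs or anxiety scores. The missing-data report accounts for 16 + 4 participants and does not show whether other dosed participants left or were left out. Its silence fits both no intolerance and unreported intolerance.

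**Conclusion.** The gap is real and should be closed. Stopping or leaving for side effects has no place among the tolerability outcomes, and the scheduled measures after Visit 2 depend on attendance from Day 5 on. If intolerance differs between sprays and some intolerant participants leave unscored, the comparison is biased toward no difference. If oxytocin is the worse tolerated spray, it will look better tolerated than it is.

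The size cannot be computed from the documents and may be zero. The 37.5% planned loss is an upper bound on the share affected, not an estimate. The fall from 10 points to between 8.1 and 0 rests wholly on the assumed intolerance rates, on equal k on both sprays, and on the side effects of those who leave not being counted.

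**What to change.** - **SAP, Outcomes paragraph.** Add as a named tolerability outcome the number and proportion who stopped each spray course early, for any reason and for a side effect. The denominator is everyone who took one dose or more of that course. Compare oxytocin with placebo, paired where both courses were started, with a risk difference and confidence interval.
- **Same paragraph.** State that AEs reported by telephone or at withdrawal are counted under the spray in use at the time.
- **SAP, attrition sentence and Missing data reporting.** Report attrition after the first dose by spray course, with reasons, and state zero if there was none.

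This needs SAP wording and one small table, and it changes no clinical rule. The SAP speaks of completed analyses and a locked database, so the table should be labelled as a later addition if it is one.

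There are three costs. The result may make tolerability look less favourable. It will be imprecise at about 16 pairs: even 0 of 16 stopping leaves a two-sided 95% exact upper limit of 1 − 0.025^(1/16) = 20.6%. For those who leave before Day 5, the data must come from call and withdrawal records, because Table 1 schedules medication accountability only at Visits 3 to 6. Whether those records are complete should be checked first.
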